CooperVision

FINAL

Fitting Evaluation of Hydrogel and Silicone Hydrogel Sphere Design Contact Lenses.

Sponsor Study Code: EX-MKTG-79
Protocol Date: January, 2017
Sponsor Company: CooperVision, Inc.
Document Type: Protocol
Study Category: Post Market
Start Date: February, 2017
Finish Date: March - April, 2017
Clinical Site: School of Optometry Clinic, National Autonomous University (UNAM), Mexico City

Protocol Sponsor: [REDACTED]

Site Principal Investigator: [REDACTED]

Revision History

Document number	Date	Comments
EX-MKTG-79	1/12/2017	First draft (v 1.0)
EX-MKTG-79	1/13/2017	Second draft (v 2.0)
EX-MKTG-79	1/13/2017	Final

Confidential

EX-MKTG-79 Fitting Evaluation of Hydrogel and Silicone Hydrogel Sphere Design Contact Lenses.

PERSONNEL & FACILITIES

STUDY SPONSOR: CooperVision Inc.
[name]
[name]

SPONSOR COORDINATOR: [REDACTED]
[REDACTED]
[REDACTED]
[REDACTED]

SITE PRINCIPAL
INVESTIGATOR: [REDACTED]
[REDACTED]
[REDACTED]
[REDACTED]

STATISTICAL ADVISOR: [REDACTED]
[REDACTED]
[REDACTED]
[REDACTED]

STUDY MONITOR: [REDACTED]
[REDACTED]
[REDACTED]
[REDACTED]

Protocol Synopsis

Protocol Number	EX-MKTG-79
Title	Fitting Evaluation of Hydrogel and Silicone Hydrogel Sphere Design Contact Lenses.
Name of Device(s) and (by USAN material)	Biomedics XC (omafilcon A), Proclear (omafilcon A), Clariti® elite (somofilcon A)
Indications for Use	
Approved for use:
 
 • omafilcon A (Daily wear, monthly replacement) • somofilcon A (Daily wear, monthly replacement) 
Indication for use in this study:
 
 • daily wear for all lens types
Study Design	Prospective, non-dispensing, double masked, randomized, bilateral, daily wear in each study pair.
Purpose	The aim of this non-dispensing fitting study is to evaluate the short term lens fit, vision performance and patient subjective experiences of three monthly replacement sphere lenses.
Study Duration	
The anticipated timeline for this study is as follows:
 
 • Patient enrolment: February- March, 2016 • Visits: V1 (Dispensing), V2 (1 hour post lens settling) for each lens pair.
Patient Population	Habitual soft contact lens wearers with myopia that provide written informed consent and meet the protocol entrance criteria.
Sample Size	Target enrollment and completion is 40 subjects total.
Center Destination (Mexico)	School of Optometry Clinic, National Autonomous University (UNAM)
Number of Centers	Single Center
Patient Follow-up	
Subjects enrolled in this study will be followed up after the lens dispensing session:
 
 • Post dispensing follow-up at 1 hour for each study lens pair
Primary Endpoint	High contrast visual acuity
Secondary Endpoints	Lens fitting characteristics, subjective ratings, preference, and ocular response.

Table of Contents

1	Introduction	6
2	Study Objective	6
3	Study Hypothesis	6
3.1	Study Hypothesis	6
4	Study Design	6
5	Investigational Sites	6
5.1	Number of Sites	6
5.2	Investigator Recruitment	7
6	Ethics Review / Statement of Compliance	7
6.1	Relevant Standards / Guidelines	7
6.2	Institutional Review Board	7
6.3	Clinical Trial Registration	7
6.4	Informed Consent	7
7	Potential Risks and Benefits to Human Subjects	8
8	Materials and Methods	8
8.1	Participants	8
	Inclusion criteria	8
8.2	Study Materials	9
8.2.1	Contact lens	9
8.2.2	Contact Lens care	10
8.2.3	Storage of Study Medications/Treatments	10
8.2.4	Clinical Supply Inventory	10
8.2.5	Disposal of Consumables	10
8.2.6	Masking and Control of Study Materials	10
8.2.7	Ordering and Accountability of Study Materials	10
8.3	Visit Schedule and Procedures	11
8.3.1	Visit 1 after dispensing (Fit lenses / Evaluate [e.g. P1])	11
8.3.2	Visit 2 after 1 hour (Assess lenses / Study exit)	12
9	Adverse Event Reporting	12
9.1	Adverse Response Definitions	12
9.2	Procedures for Adverse Events	14
9.3	Reporting Adverse Events	15
9.4	Discontinuation from the Study	15
10	Statistical Analysis	15
10.1	Statistical analysis	15

11 Data Quality Assurance	16
11.1 Study monitoring.....	16
11.2 Record keeping	16
11.3 Record retention	16
11.4 Data Entry / Data Management	16
11.5 Confidentiality.....	16
11.6 Publication.....	16
12 Study Costs and Subject Compensation.....	17
13 Appendixes.....	18

1 Introduction

Biomedics XC is part of an older generation of a hydrogel contact lens portfolio from CooperVision which will be discontinued soon.

Therefore, CooperVision is interested in switching wearers of the Biomedics XC brand into the Proclear hydrogel or Clariti® elite silicone hydrogel contact lenses. A non-dispensing fitting study is proposed to evaluate the clinical performance of these lenses.

2 Study Objective

The aim of this non-dispensing study is to evaluate the short term lens fit, vision performance and patient subjective experiences of three monthly replacement sphere lenses.

The key variables of interest are:

- High contrast distance visual acuity
- Lens fitting characteristics and preference
- Subjective comfort ratings and preference
- Subjective handling ratings and preference (insertion & removal assessed by subjects)

** Lens fit preference judged by the study investigator*

3 Study Hypothesis

3.1 Study Hypothesis

- Null hypothesis (H₀): There is no difference in high contrast visual acuity, lens fitting characteristics, and subjective assessments between lens types.
- Alternative hypothesis (H₁): There is a difference in high contrast visual acuity, lens fitting characteristics and subjective assessments between lens types.

4 Study Design

This is a 40-subject, double masked, randomized, bilateral, non-dispensing fitting trial comparing hydrogel and silicone hydrogel lens materials. It is anticipated that this study will involve 2 visits for each lens pair, as follows: Visits: V1 (lens dispensing), V2 (1 hour post lens settling). Each subject will be randomized to wear each pair bilaterally in a series of three short fitting comparisons.

5 Investigational Sites

5.1 Number of Sites

This will be a single center investigational site in Mexico City. (Target 40 subjects).

5.2 Investigator Recruitment

This study will be conducted at School of Optometry Clinic; National Autonomous University (UNAM) Mexico City. The Investigators will be required to fulfil the following criteria:

- Licensed optometrist with at least two years of contact lens fitting experience.
- Experienced Investigators who will be trained in Good Clinical Practice (GCP) by the principal investigator.
- In-office email or fax.
- Willingness to follow the study protocol and to co-operate with the study monitors.

This clinical study is designed to be in conformance with the ethical principles in the Declaration of Helsinki, with the ICH guidelines for Good Clinical Practice (GCP) and all the applicable local guidelines.

6 Ethics Review / Statement of Compliance

6.1 Relevant Standards / Guidelines

This implementation document has been developed in accordance with the following:

- ICH Harmonized Tripartite Guideline for Good Clinical Practice
- Declaration of Helsinki

6.2 Institutional Review Board

This study will be conducted in accordance with Institutional Review Board regulations (U.S. 21CFR Part 56.103) or applicable IEC regulations. Copies of all IRB/IEC correspondence with the investigator/sponsor will be kept on file. The study will commence upon approval from the following Ethics Committee: Comisión de Ética de la FESI. [name]. [contact] and email address [contact].

6.3 Clinical Trial Registration

This study will be registered with clinical trials.gov in accordance with section 801 of the Food and Drug Administration (FDA) Act which mandates the registration of certain clinical trials of drugs and medical devices.

6.4 Informed Consent

Informed consent, (Appendix 1), shall be obtained in writing from the subject and the process shall be documented before any procedure specific to the clinical investigation is carried out.

7 Potential Risks and Benefits to Human Subjects

There may be direct benefits to the subjects in this study such as improved vision, comfort, convenience, and cosmetic advantage. Participation in a study may contribute to scientific research information that may be used in the development of new contact lens products. In addition, subjects will receive an examination of the front part of their eyes and may have the opportunity to try a different type of soft contact lenses and/or different lens care products at no cost to them. The contact lens materials used in this study are commercially available intended for daily wear (NOT extended wear) similar to the average wearing time of 10-16 hours for daily wear lenses.

This study is considered to be a non-significant risk study based on United State Food and Drug administration (FDA) and International Standards Organization (ISO) guidelines because the study devices used as intended in this study (daily wear) don't represent a potential for serious risk to the health, safety or welfare of the subject, and (2) it is not an implant, (3) it is not used to support or sustain human life, (4) it is not of substantial importance in diagnosing, curing, mitigating or treating disease or otherwise prevents impairment of human health, (5) does not present a potential for serious risk to the health, safety or welfare of the subject.

Complications that may occur during the wearing of contact lenses include discomfort, dryness, aching or itching eyes, excessive tearing, discharge, hyperemia and variable or blurred vision. More serious risks may include photophobia, iritis, corneal edema or eye infection. Although contact lens-related infections are very infrequent, the possibility does exist. The incidence of infection due to day-wear soft lenses is 0.035%. Almost always an infection will occur only in one eye. This risk is assumed by 35-million Americans who currently wear contact lenses. Routine clinical procedures including auto-refraction, auto-keratometry, visual acuity, anterior ocular health assessment, and contact lens fitting will be used. In addition, high magnification imaging of the lens fit may be made using 35 mm or digital cameras, in vivo confocal microscopy, and/or specular microscopy.

Patients will be monitored in the clinic during the study to reduce if not eliminate the occurrence of adverse or potential adverse events. Patients will be given instructions from the study investigator regarding early symptoms and signs of adverse events and their contact information.

8 Materials and Methods

8.1 Participants

Adapted soft contact lens wearers with myopia will be recruited for the study for a minimum of **40** completed. Subjects will be recruited from the National Autonomous University School of Optometry databases who agree to voluntarily participate in the study (Appendix 2, timeline). All subjects will be screened to determine study eligibility. Each subject will be given a unique ID number. Additionally, all subjects must meet the study inclusion and exclusion criteria listed below.

Inclusion criteria

A person is eligible for inclusion in the study if he/she:

- Is between 18 and 40 years of age (inclusive).
- Has had a self-reported visual exam in the last two years.
- Is an adapted soft CL wearer who is not wearing any of the study lenses.

- Has a CL spherical prescription between - 1.00 and - 6.00 (inclusive)
- Has a spectacle cylinder up to 0.75D in each eye.
- Can achieve best corrected spectacle distance visual acuity of 20/25 (0.10 logMAR) or better in each eye.
- Can achieve a distance visual acuity of 20/30 (0.18 logMAR) or better in each eye with the study contact lenses.
- Has clear corneas and no active ocular disease.
- Has read, understood and signed the information consent letter.
- Patient contact lens refraction should fit within the available parameters of the study lenses.
- Is willing to comply with the wear schedule.
- Is willing to comply with the visit schedule.

Exclusion Criteria

A person will be excluded from the study if he/she:

- Has never worn contact lenses before.
- Currently wears rigid gas permeable contact lenses.
- Has a history of not achieving comfortable CL wear (5 days per week; > 8 hours/day)
- Has a CL prescription outside the range of - 1.00 to - 6.00D
- Has a spectacle cylinder \geq 1.00D of cylinder in either eye.
- Has contact lens best corrected distance vision worse than 20/25 (0.10 logMAR) in either eye.
- Presence of clinically significant (grade 2-4) anterior segment abnormalities.
- Presence of ocular or systemic disease or need of medications which might interfere with contact lens wear.
- Slit lamp findings that would contraindicate contact lens wear such as:
 - Pathological dry eye or associated findings
 - Pterygium, pinguecula, or corneal scars within the visual axis
 - Neovascularization > 0.75 mm in front of the limbus
 - Giant papillary conjunctivitis (GCP) worse than grade 1
 - Anterior uveitis or iritis (past or present)
 - Seborrheic eczema, Seborrheic conjunctivitis
 - History of corneal ulcers or fungal infections
 - Poor personal hygiene
- Has a known history of corneal hypoesthesia (reduced corneal sensitivity)
- Has aphakia, keratoconus or a highly irregular cornea.
- Has Presbyopia or has dependence on spectacles for near work over the contact lenses.
- Has undergone corneal refractive surgery.
- Is participating in any other type of eye related clinical or research study.

8.2 Study Materials

8.2.1 Contact lens

All subjects will be trial fitted and, if suitable, dispensed the first pair of lens brand assigned per a predetermined randomization table (Appendix 3). The lenses used in this study are all FDA approved

Confidential

9

and marketed products. Details of the study contact lenses are shown in Table1 and will be provided by the Sponsor.

Table1: Study lens parameters

Brand	Biomedics XC	Clariti Elite Aspheric	Proclear Monthly
Manufacturer	CooperVision	CooperVision	CooperVision
Material	Omafilcon A	Somofilcon A	Omafilcon A
WC %	60%	56%	62%
Base Curve	8.5	8.6	8.6
Lens Diameter	14.2	14.2	14.2
Lens Powers	-1.00 to - 6.00 (in 0.25 steps)	-1.00 to - 6.00 (in 0.25 steps)	-1.00 to - 6.00 (in 0.25 steps)
Replacement schedule	Daily	Daily	Daily

8.2.2 Contact Lens care

Since this is a non-dispensing fitting study no contact lens care will be required.

8.2.3 Storage of Study Medications/Treatments

There are no unapproved investigational products used in this study requiring special storage accommodations.

8.2.4 Clinical Supply Inventory

There are no unapproved investigational products used in this study requiring special inventory requirements.

8.2.5 Disposal of Consumables

This study dispenses consumables (lenses) to participants for use during the study. Study lenses worn by participants will be discarded by the principal investigator at the end of the study.

8.2.6 Masking and Control of Study Materials

The study contact lenses will be masked to both the subject and the investigator. The study lenses will be removed from their blister pack by an assistant and transferred to an unmarked lens case to maintain subject and investigator masking of the study lenses. Next, subjects will be instructed to insert the lenses directly from the lens case.

8.2.7 Ordering and Accountability of Study Materials

The study sponsor will supply the investigators with the study lenses to use during the study.

8.3 Visit Schedule and Procedures

This will be a randomized, double masked, bilateral, non-dispensing fitting study. Participants will be examined at two different points over the course of one day, V1 (lens dispensing), V2 (1 hour post lens settling). They will wear three different pairs of lenses in randomized fashion. Anterior ocular health examination will be performed at baseline without the use of fluorescein*.

Next, the study lenses will be dispensed and fit evaluated. After 1 hour of wear, lens fit assessments will be collected and the lenses removed. Anterior ocular health examination will be performed with fluorescein and the subjects exited from the study. This same procedure will be repeated at a different day for each lens pair.

** Fluorescein will not be used before lens dispensing to prevent potential eye discomfort that could influence subjective comfort ratings after lens fitting and settling. However, fluorescein will be instilled at the 1 hour visit upon lens removal.*

The following outline identifies the two study visits and the general procedures, (Appendix 5), to be conducted at each visit for each day of the study and recorded in the case report forms (Appendix 6):

8.3.1 Visit 1 after dispensing (Fit lenses / Evaluate [e.g. P1])

- Explanation of the study
- Sign informed consent form
- Anterior ocular health examination (Slit lamp without fluorescein)
- Insert lenses from pair # 1
- Visual acuity
 - High contrast, monocular logMAR
 - High contrast, binocular log MAR
- Subjective assessments
 - Handling on insertion (0 -100 scale). **Subject to insert study lenses and rate handling.**
 - Comfort on insertion (0 -100 scale)
 - Burning/stinging (0 – 100 scale)
 - Comfort preference (right vs. left)
- Lens fit assessment
 - Lens centration (optimum, decentration acceptable, decentration unacceptable)
 - Corneal coverage [Y/N]
 - Post blink movement (0-5 Likert scale)
 - Lens tightness on push-up test (0% - 100% in 5% steps)
 - Overall fit acceptance (0 – 4) and reason if Grade 2 or less.
 - Investigator's fit preference

8.3.2 Visit 2 after 1 hour (Assess lenses / Study exit)

- Subjective assessments
 - Comfort on insertion (0 -100 scale)
 - Comfort preference (right vs. left)
 - Handling on removal (0 -100 scale)
- Lens fit assessment
 - Lens centration (optimum, decentration acceptable, decentration unacceptable)
 - Corneal coverage [Y/N]
 - Post blink movement (0-5 Likert scale)
 - Lens tightness on push-up test (0% - 100% in 5% steps)
 - Overall fit acceptance (0 – 4) and reason if Grade 2 or less.
 - Investigator's fit preference
 - Lens removal by subject
- Anterior ocular health examination with fluorescein
- Study exit form must be completed
- Subjects will be required to come to the clinic on a separate day to be fitted with the other study lenses.
- The same procedure as section 8.3.1 and 8.3.2 will be performed for the rest of the lens pairs.

9 Adverse Event Reporting

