10.1 Statistical analysis

Summary statistics will be produced, (e.g. mean, standard deviation), by the principal investigator ([name]). Differences between lenses will be compared using Paired t-tests. Paired t-tests /analysis of variance for normal (interval/continuous) data, Wilcoxon's signed ranks test for non-normal (ordinal) data, chi-squares test for nominal data. A Chi-Square test will be used to evaluate lens preference questions.

A sample size of 33 subjects was calculated which provides 80% power to detect a difference of half a line in logMAR high contrast visual acuity (HCVA). The critical alpha level for statistical significance will be set at $p \leq 0.05$, with adjustment for multiple comparisons. All participants who are evaluated in the study will be used in the analysis. In the event of missing data, individual numbers points will be excluded in the analysis and not extrapolated from the collected data.

11 Data Quality Assurance

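### The only 0–100 comfort rating at the 1-hour visit is labelled as insertion comfort, so the section 8.3 outline names no settled comfort score; separately, the primary acuity measure and time point should be stated

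*Combined protocol and SAP*

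**What the plan says.** **Comfort.** Section 2 lists "Subjective comfort ratings and preference" among the key variables. Section 8.3.1 (Visit 1) has one 0–100 comfort item, and section 8.3.2 (Visit 2, after 1 hour) also has one. Both read "Comfort on insertion (0 -100 scale". The only other comfort item at either visit is a right-versus-left preference. The footnote in section 8.3 explains that fluorescein is not used before the lenses go in, because discomfort from it "could influence subjective comfort ratings after lens fitting and settling". Section 8.3 introduces the two lists as the procedures to be carried out at each visit and recorded on the case report forms, with detail in Appendices 5 and 6.

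**Vision.** The synopsis gives the primary endpoint as "High contrast visual acuity" and states no time point. Section 8.3.1 lists two acuity items after insertion, "High contrast, monocular logMAR" and "High contrast, binocular log MAR". Section 8.3.2 lists none. Section 10.1 bases the sample size of 33 on "80% power to detect a difference of half a line in logMAR high contrast visual acuity (HCVA", again without saying which of the two measures is meant or when it is taken. It promises a multiplicity adjustment but names no method.

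**Design.** Section 4: "Each subject will be randomized to wear each pair bilaterally in a series of three short fitting comparisons".

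**The concern.** The label on the 1-hour comfort item and the footnote describe different quantities. The footnote speaks of a rating given once the lens has settled; the label asks about insertion. A subject asked at 1 hour to rate comfort on insertion may answer from memory of the first moments, or may rate how the lens feels now. The data would not show which. A 1-hour score collected under that label could not be clearly reported as settled comfort, and it cannot be recovered once the lenses are out. Comfort is one of the outcomes meant to inform moving Biomedics XC wearers to the other two lenses.

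The acuity question is one of scope. Fit will be described at both visits, but vision, the primary endpoint, at Visit 1 only. The plan also leaves open which acuity measure the primary comparison uses.

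**Working it through.** **1. The two visit lists side by side (sections 8.3.1 and 8.3.2)**

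| Item | Visit 1 | Visit 2 (1 hour) |
|---|---|---|
| 0–100 comfort | insertion label | same insertion label |
| Right/left comfort preference | yes | yes |
| 0–100 handling | on insertion | on removal |
| Burning/stinging | yes | no |
| Fit items (centration, coverage, movement, push-up tightness, overall acceptance, investigator preference) | 6 | 6 |
| Acuity items (monocular, binocular) | 2 | 0 |

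The handling label changes from insertion to removal and burning/stinging is dropped, so labels in this outline do carry timing. The comfort label was not changed with them. One of one 0–100 comfort items at Visit 2 has the insertion label.

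**2. Whether another item fills the gap.** The right/left preference does not. Section 4 has each pair worn bilaterally, so both eyes wear the same lens type and the item compares eyes, not lenses.

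**3. Reach of the label.** 40 subjects × 3 lens pairs = 120 one-hour visits. This counts where the label applies. It does not count scores known to be lost.

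**4. Number of primary comparisons.** Three lenses give 3 × 2 / 2 = 3 pairs.
- One measure, one time point: 3 × 1 × 1 = 3.
- Both acuity measures as now listed, if both are tested: 3 × 2 × 1 = 6.

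With Bonferroni purely as an example, the thresholds are 0.05/3 = 0.0167 and 0.05/6 = 0.0083, so the choice of measure affects the threshold. Adding a 1-hour acuity without ranking the measures would give 3 × 2 × 2 = 12. That number would come only from the addition; it does not describe the present plan.

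**5. The plan's sample size.** The SD of paired differences is not given, so 33 cannot be reproduced directly. Assume half a line is 0.05 logMAR (one line = 0.10) and a two-sided alpha of 0.05. The paired formula is n = (SD × (1.960 + 0.842) / 0.05)². With an assumed SD of 0.10 this is (0.10 × 2.802 / 0.05)² = 31.4, that is 32 subjects; the exact t-test gives 34. Back-solving from 33 gives an SD of about 0.103 (normal) or 0.099 (t-test). For assumed SDs from 0.08 to 0.12 the t-test n runs from 23 to 48. The stated 33 is plausible but unverifiable. Moving the primary acuity to 1 hour would alter it only if the SD there differed, and the documents give no SD at either time.

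**6. Site time for a 1-hour acuity.** At an assumed 2 to 5 minutes per visit (not in the documents), 120 × 2 = 240 minutes = 4 hours and 120 × 5 = 600 minutes = 10 hours. Per subject, 3 × 2 = 6 to 3 × 5 = 15 minutes over three days.

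**The case against.** On comfort, the strongest reply is that this is a label slip. The item sits under the 1-hour heading, the lenses are inserted once per pair, and the footnote shows what was meant. Appendices 5 and 6, which decide what subjects are actually asked, may already have the right words. Most of this stands: the intent is reasonably clear, and a reader who infers that settled comfort will certainly be lost goes beyond the documents. It does not remove the point. Section 8.3 makes this outline the list that is conducted and recorded, and its label contradicts its own footnote. If the appendices are right, section 8.3 still has to match them.

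On vision, a reader might infer that Visit 2 acuity was promised and then omitted, or that acuity on freshly inserted lenses biases the comparison. The documents support neither reading. No section promises acuity at 1 hour, and the section 8.3 narrative names only fit at that point, in agreement with section 8.3.2. All lenses are tested at the same visit, so the comparison between them there is valid. Nothing shows that acuity changes over the hour, or changes differently by lens. It is not even established that the lenses are wholly unsettled at Visit 1. Section 8.3.1 gives no minutes between insertion and acuity, its bullets are not a reliable clock (handling on insertion is listed after acuity), and the description of Visit 2 could be read as an hour after settling. The imbalance of six fit items repeated against no acuity items is a count of items and does not measure error.

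**Conclusion.** The comfort label is wrong as written and should be corrected. It affects the only 0–100 comfort item at each of 120 planned one-hour visits, and read literally it leaves a key variable without a settled score. This rests on the visible section 8.3 outline alone; Appendices 5 and 6 were not seen.

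The acuity timing is not an error. A 1-hour measurement would be a cheap improvement in scope, and a plain statement that the vision result applies to Visit 1 would also be enough. No bias or size of effect is claimed.

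The unspecified choice between monocular and binocular acuity is a present gap in the primary endpoint, whether or not a 1-hour measurement is added. As listed, the primary comparisons could number three or six.

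**What to change.** 1. In section 8.3.2 and the matching CRF field, relabel the item *Comfort at 1 hour, before lens removal (0–100)*, and check Appendices 5 and 6 for the same wording. Cost: wording only.

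2. Optional: repeat the Visit 1 acuity at Visit 2, before lens removal and fluorescein. There are no extra visits; the added time is that in step 6 of the working, on its assumed minutes. If this is not adopted, state in the protocol and report that the vision conclusion applies to the Visit 1 time point only, which costs one sentence.

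3. Whichever branch of step 2 is taken, name one acuity measure (monocular or binocular) and one time point as primary in the synopsis and section 10.1 before data collection, with any other acuity results secondary. The primary lens comparisons then number three. The edit is short but the choice defines the endpoint on which the sample size rests, so the sponsor and statistical advisor should make it deliberately and confirm that the SD behind the 33 subjects refers to that measure and time.
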